5.4.4.3 Conclusion

The results from both adult (Phases I-III) and pediatric Phase I trials of high-dose oral fenretinide suggest that peak plasma levels exceeding 10 µM can be achieved with tolerable toxicity.

Prolonged periods of fenretinide treatment (up to 5 years) in the cancer prevention studies were associated with fenretinide steady-state peak plasma concentrations of 1-2 µM at daily doses of 200 to 400mg and no significant toxicity/safety concerns. In the cancer treatment studies in children the peak plasma concentrations reached 14.5 µM with relatively mild adverse effects. In general, no significant toxicity was observed in children with peak plasma levels below 3µM. The incidence and severity of the most commonly observed toxicities related to fenretinide treatment such as nyctalopia, headache, dry eye, cutaneous, ungual, or mucosal toxicities observed in patients with 3–10 µM peak levels increased at peak levels >10µM. The adverse events were resolved after dose reduction or after discontinuation of the treatment. Maximum tolerated dose was not reached in children with neuroblastoma at daily doses of 4000mg/m² and fenretinide plasma peak levels of 14.5 µM.

Fenretinide is reducing plasma retinol levels and retinol binding protein potentially leading to development of symptoms of nyctalopia in some patients. This effect was rarely dose limiting, and quickly reversible following dose reduction or discontinuation of treatment. Moreover, this effect does not seem to be proportional to the dose. In previous fenretinide clinical studies a drug free period of 3-7 days following a 28-day oral exposure was proven to help prevent or alleviate nyctalopia and was integrated in all clinical studies.

There were no serious adverse events related to fenretinide recorded in the study, and the overall number of adverse events tended to decrease with the increase of the dose. The incidence of nyctalopia symptoms reported in this study is consistent with the incidence of symptoms of diminished dark adaptation reported in other clinical trials with fenretinide. Ad-hoc and scheduled ophthalmological examinations did not reveal any abnormality or signs of retinal damage in these patients. The reduction of serum retinol levels, as compared to baseline, appears to be smaller in CF patients than other patient populations for which lower doses of fenretinide were used.

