3 STATISTICAL METHODS

3.1 Statistical Handling Policy

3.1.1 Analysis Conventions

This section details general guidelines to be used for the statistical analyses. Deviations from these general policies may be given in the specific detailed sections of this statistical analysis plan. When this situation occurs, the rules set forth in the specific section take precedence over the general conventions. The following policies will be applied to all data presentations and analyses:

- Two-tailed tests will be performed for all analyses that use statistical testing with a significance level of $\alpha = 0.05$
- All p-values will be rounded to 4 decimal places (SAS format p-value). All p-values that round to 0.000 will be presented as '<0.001' and p-values that round to 1.000 will be presented as '>0.999'.
- Summary descriptive statistics will consist of the number and percentage of responses in each category for discrete variables, and the mean, median, standard deviation (SD), minimum, maximum, and 95% confidence interval for continuous variables.
- All mean and median values will be formatted to one decimal place. Standard deviation values will be formatted to two decimal places.
- All percentages will be rounded to one decimal place. Where appropriate, the number and percentage of responses will be presented in the form XX (XX.X %), where the percentage is in the parentheses.
- All listings will be sorted for presentation in order of treatment group, site number, subject number, and date of procedure or event.
- When necessary for analysis purposes, partial dates will be completed (i.e., turned into complete dates) using the most conservative approach. Where appropriate, all analyses and summary tables will have the population sample size for each treatment group in the column heading.

- Tables will include titles with the corresponding analysis population and footnotes describing the analyses involved, and listings of covariates included in the analyses, where relevant.
- In order to maintain vertical alignment, all tables and listings will be incorporated into MS Word and an 8-point Courier New font will be used.
- Version 9.4 (or later) of SAS® will be the statistical software package used to produce all summaries, listings, statistical analyses, and graphs.
- Version 20.0 (or higher) of MedDRA will be used for adverse event and pre-treatment conditions coding.

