3.3 Analysis Population

The Intent-to-treat (ITT) Population will include all patients randomized to a treatment group who complete the baseline evaluations, regardless of having received any study treatment or not. The ITT population will be used for the primary analyses of all study endpoints, taking into consideration the specific populations described below. The patients will be kept in their randomized treatment arm for the analyses.

The Per Protocol (PP) Population will include all patients randomized to a treatment group to whom at least 5 cycles of study treatment are administered in accordance with the protocol, defined as at least 80% compliance. The PP population will serve as the basis for secondary analyses of

all study endpoints, taking into consideration the specific populations described below. The patients will be kept in the treatment arm that they actually received for the analyses.

The FEV₁ Population is a subset of the PP population and will include all patients who have validated FEV₁ values (values judged to be obtained from adequate expiratory curves by central review) for at least 4 time points of the study comprising at the minimum the baseline and Day 161 assessments. This population will be used for the secondary analyses of all FEV₁-related endpoints. The patients will be kept in the treatment arm that they actually received for the analyses.

The Protocol-Defined PEx Subset Population will include all patients who experience a protocol - defined PEx episode (\geq 4/12 Fuch symptoms and use of IV antibiotic) during the study after completing at least one cycle of study drug treatment. The patients will be kept in the treatment arm that they actually received for the analyses.

The Overall PEx Subset Population will include all patients who experience an oral or IV antibiotic treated PEx episode during the study after completing at least one cycle of study drug treatment. The patients will be kept in the treatment arm that they actually received for the analyses.

The Safety Population will include all patients randomized to a treatment group who received at least one dose of study drug treatment. This population will serve as the basis for analyses of all safety endpoints. The patients will be kept in the treatment arm that they actually received for the analyses.

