3.10 Ophthalmologic Examinations and Night Vision Questionnaire

The answers to the NVQ questionnaires and the resulting levels will be summarized by treatment group. The results (normal/abnormal, new adverse findings) of the planned during- and post-study ophthalmologic examinations will be presented, alongside the baseline examination and summarized by treatment group. Ad-hoc examinations and findings will also be presented alongside the baseline examination. All reported symptoms of nyctalopia and hemeralopia will be tabulated by treatment group. Reported symptoms confirmed by objective measures will be tabulated separately by treatment group. Individual data will be presented in listings.

No statistical analyses of ophthalmologic data are planned

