- TEAEs leading to treatment discontinuation;
- Serious TEAEs;
- Fatal TEAEs.

All safety analyses will be performed on the Safety population.

Additional Safety Evaluations

The following safety evaluations, listed below, will be performed per the methodology stipulated in each of the respective sections provided:

- Clinically relevant changes from baseline in vital signs (for more details, please see Section 3.7);
- Clinically relevant changes from screening in 12-lead ECG (for more details, please see Section 3.7);
- Clinically relevant changes from baseline in physical examinations (for more details, please see Section 3.7);
- Clinically relevant changes from baseline in safety laboratory assessments (hematology with differential count, biochemistry, and urinalysis) (for more details, please see Section 3.8);
- Plasma retinol and retinol-binding protein values, changes from screening/baseline, correlated with ophthalmological symptoms, specifically symptoms of nyctalopia. More precisely, Spearman correlation between plasma retinol and retinol-binding protein concentrations (change-from-baseline to Week 24) and the cumulative number of AEs for “nyctalopia” will be presented in scatter plot figures along with the regression line. Nyctalopia will be identified according to AEs of the following SOC/PT/LLT: Eye disorders/ Night blindness/ Nyctalopia.
- Change in PEx incidence and antibiotic treatment requirement (for more details, please see Section 3.14).

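### SAP 3.18 correlates retinol/RBP change with nyctalopia on a population holding both arms and gives no arm split, so the coefficient and line may only restate the treatment effect

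*SAP*

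**What the plan says.** The analysis is one bullet under the additional safety evaluations in SAP 3.18: "More precisely, Spearman correlation between plasma retinol and retinol-binding protein concentrations (change-from-baseline to Week 24) and the cumulative number of AEs" for nyctalopia. The results "will be presented in scatter plot figures along with the regression line". The same section states "All safety analyses will be performed on the Safety population", and SAP 3.3 defines that set: "The Safety Population will include all patients randomized to a treatment group who received at least one dose of study drug treatment". The definition adds "The patients will be kept in the treatment arm that they actually received for the analyses".

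The bullet does not say whether the correlation is run by arm, on LAU-7b patients only, stratified by arm, or on everyone together. SAP 3.8 (vital signs and ECG), 3.9 (laboratory values), 3.10 (ophthalmology and NVQ) and 3.11 (retinol/RBP categories) each specify presentation by treatment group. Protocol 12.5 lists the same correlation and is also silent on arm.

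On what the drug is expected to do, Protocol 5.4.4.3 says "Fenretinide is reducing plasma retinol levels and retinol binding protein potentially leading to development of symptoms of nyctalopia in some patients". Protocol 5.4.5.2 likewise treats symptomatic, reversible nyctalopia as a known effect of fenretinide, through RBP binding and lower retinol.

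The correlation is listed among the exploratory endpoints (Protocol 7.1.4, SAP 2.8.1.3). SAP 3.10 states "No statistical analyses of ophthalmologic data are planned".

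**The concern.** The useful question is whether patients whose retinol or RBP falls further report more night-vision problems. A coefficient computed across both arms does not isolate that. If LAU-7b moves retinol down and nyctalopia reports up, the arms form two clusters, one with little retinol change and few events and one with lower retinol and more events. A line through both slopes downward even if, among treated patients, retinol change says nothing about who has symptoms. Perfectly timed retinol samples would not prevent this.

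At stake is how one safety figure is read. A sloped line and a negative coefficient could be taken as evidence that retinol or RBP marks individual risk, when they may only repeat that LAU-7b lowers retinol and that LAU-7b patients report more nyctalopia. Both facts already appear in the by-arm tables. The documents leave the patient-level link open. Protocol 5.4.4.3 says the effect does not seem proportional to dose, and Protocol 5.4.4.1 reports that no symptom in Phase Ib was confirmed by objective measurement.

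**Working it through.** The plan gives no sample size, coefficient or error rate for this correlation, so there is no figure of its own to reproduce. The check asks what a pooled coefficient would show if there were no relation within either arm.

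**Inputs**
- From the documents: 1:1 allocation, 136 randomised (68 per arm), at least 60 completers per arm (SAP 2.4 and 2.6). Direction of effect: retinol/RBP down and nyctalopia up on LAU-7b (Protocol 5.4.4.3 and 5.4.5.2).
- Assumed, because the documents give no figure for this dose in CF: a retinol shift d of 0 to 2 within-arm SD, and the proportion of patients with any nyctalopia AE, p0 on placebo and p1 on LAU-7b.

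**Closed form.** Retinol change is taken as Normal with SD 1 and mean 0 on placebo, -d on LAU-7b. AE counts are treated as any versus none, which is nearly exact when repeat events are few. Ranks are expressed as fractions, with SD √(1/12) = 0.2887.

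- Difference in mean fractional rank of retinol change, LAU-7b minus placebo: Δr = 1/2 - Φ(d/√2).
- Difference in AE proportion: Δp = p1 - p0. Mean proportion: p̄ = (p0 + p1)/2.
- With equal arms and zero within-arm association, the pooled covariance comes only from the arm difference and equals (1/4)·Δr·Δp. Hence

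ρ(pooled) = (1/4)·Δr·Δp / [0.2887·√(p̄(1 - p̄))].

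Worked example, d = 1 and 5% versus 15%: Φ(0.707) = 0.760, so Δr = -0.260; Δp = 0.10; p̄ = 0.10, so √(p̄(1 - p̄)) = 0.300. Then ρ = 0.25 × (-0.260) × 0.10 / (0.2887 × 0.300) = -0.0065 / 0.0866 = -0.075.

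| d (SD) | Placebo / LAU-7b | Closed form | Simulated mean ρ |
|---|---|---|---|
| 0 | 5% / 20% | 0 | 0.00 |
| 1 | 5% / 5% | 0 | 0.00 |
| 0.5 | 5% / 10% | -0.023 | -0.022 |
| 1 | 5% / 10% | -0.043 | -0.045 |
| 1 | 5% / 15% | -0.075 | -0.07 |
| 1 | 5% / 20% | -0.102 | -0.101 |
| 1 | 5% / 25% | -0.126 | -0.13 |
| 1.5 | 5% / 25% | -0.173 | -0.17 |
| 2 | 5% / 25% | -0.204 | -0.20 |

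Rows with 15% or 25% on LAU-7b were simulated with 68 per arm (2000 runs), the others with 60 per arm (4000 runs). The within-arm relation was zero throughout. The first two rows show that both variables must shift for the artefact to appear.

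**If a nominal p-value were printed.** SAP 3.1.1 would make it two-sided at 5% ("Two-tailed tests will be performed for all analyses that use statistical testing with a significance level of" 0.05). With 60 per arm and zero within-arm relation, the pooled coefficient would be significant in 5.2% of runs at 0.5 SD with 5%/10%, 7.8% at 1 SD with 5%/10%, 19.4% at 1 SD with 5%/20%, and 44.6% at 2 SD with 5%/20%. Over all scenarios run with 60 per arm, an arm-stratified coefficient stays at 4.3-5.6% and a LAU-7b-only coefficient at 3.9-5.4%.

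**The case against.** The strongest reply is that the SAP never says the arms are combined. Naming the Safety population says who is included, not that arms are merged. Exposure (SAP 3.5) and compliance (SAP 3.12) use the same population and are reported by treatment group. The population definition keeps patients in the arm received, and Protocol 12 promises data summaries by treatment group. The figure shells in SAP section 7 could show arm-specific panels, and they are not in the text available for review. This stands. Pooling is the plain reading of a bullet that omits the phrase used in SAP 3.8 to 3.11 and refers to one regression line, but it remains an inference.

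A reader might also infer that the plan contains a hypothesis test with an inflated type I error. The documents do not support that. SAP 3.18 names no p-value or decision rule for this correlation. SAP 3.10 plans no statistical analysis of ophthalmologic data. SAP 3.2 treats non-primary analyses as signal detection. What survives is that the coefficient and the slope, which are the planned output, are biased as descriptions of a patient-level relation whether or not anyone tests them.

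A reader might further infer that treatment decisions hang on this correlation, because Protocol 11.2 lets retinol/RBP measurements support decisions about ophthalmological events. That text concerns individual patients' values during the trial, not the end-of-study coefficient.

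Finally, drug-induced retinol loss may be the mechanism, so removing the arm difference could be said to remove the effect of interest. But if the mechanism works at patient level, larger falls should go with more symptoms among LAU-7b patients, where the stratified coefficient can still show it, over a narrower range of retinol change. The pooled coefficient cannot distinguish that from two arm averages.

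**Conclusion.** The point holds as a weakness in an exploratory, descriptive safety analysis. Read literally, SAP 3.18 pools two arms that the documents expect to differ on both variables, and the resulting negative coefficient could be pure treatment effect.

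Its size rests on assumed shifts and incidences: a mean pooled ρ of about -0.07 to -0.20 for 1 to 2 SD with nyctalopia in 5% versus 15-25%, and about -0.02 for 0.5 SD with 5% versus 10%. The lower end cannot be ruled out, since Protocol 5.4.4.1 reports a smaller retinol fall in CF than in other populations.

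The documents do not establish that pooling is the definite intention, that a formal test is planned, or that any trial decision depends on the result. The primary FEV1 conclusion is unaffected.

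**What to change.** In SAP 3.18, state that the Spearman coefficient for retinol and for RBP is computed within each arm, with the LAU-7b arm the one interpreted. The placebo arm will probably have too few events to be informative: at an assumed 5%, 0.05 × 60 = 3 patients. Alternatively, specify one arm-stratified (partial) Spearman coefficient with its 95% CI. Draw the scatter plot with arm-specific symbols and lines, say whether a p-value will be shown, and align the section 7 mock figure if it differs. If that figure already separates the arms, one clarifying sentence closes the point.

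The cost is a sentence and a relabelled figure. A within-arm estimate is less precise: using tanh(1.96/√(n - 3)) for a coefficient near zero, the 95% half-width is about 0.25 with 60 patients against 0.18 with 120. The stratified version keeps most of that precision. Both half-widths are approximate, given the many tied zero counts.

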Fenretinide has been safely administered in chemoprevention trials up to dose of 300 mg per day (1-1.5 μM plasma levels) for prolonged periods of time from 6 months to 5 years in large cancer populations with no significant toxicity^{69, 77, 78, 79, 80, 81}. Mild grade of nyctalopia and dermatologic disorders (dry skin, pruritus) were the most common side-effects of fenretinide treatment; rate of occurrence of both types of events tended to decrease with time or to recover spontaneously during the treatment period or shortly after cessation of dosing. Fenretinide plasma concentration (12 h post dose) at steady state was estimated to be $\sim 1 \mu\text{M}$ at 200mg dose and $\sim 1.5 \mu\text{M}$ at 300 mg dose. Adverse effects typical of other retinoids, such as decreased bone density, ligament calcification, and skeletal hyperostosis were not observed in these studies. Even after five years of therapy, abnormalities in night vision improved significantly after 7 days off therapy, and completely resolved one month after stopping fenretinide; plasma retinol concentrations returned to normal in one month following discontinuation of fenretinide^{80, 81}.

Single and repeat daily dose PK studies with fenretinide softgel formulation in healthy subjects and patient population indicate that fenretinide plasma exposure (C_{max} , AUC) also increased upon repeat daily dosing to reach a steady state level at 4-5 days^{82, 74, 83}. Presence of food increased significantly the plasma levels of the drug and has been used since as standard recommendation for fenretinide dosing⁷⁴. The increase in exposure was dose proportional up to 800mg. Plasma exposure on Day 21 with 300mg/day dose of LAU-7b formulation in adult CF patients was approximately equivalent to the exposure at the dose of 800mg on Day 28 in healthy adults with the softgel formulation, indicating an increase in fenretinide bioavailability by a factor of >2 with LAU-7b.

High-dose clinical trials

Phase I trials of high-dose (up to 14.5 μM plasma levels) oral fenretinide in pediatric solid tumors have been conducted with the corn-oil softgel formulation^{76, 79, 84}.

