7.1.4 Exploratory Endpoints

- The change from pre-study in AA, DHA and EPA in phospholipids and metabolipidomic markers (eicosanoids and docosanoids), LAU-7b compared to placebo;
- The change from pre-study in plasma oxidative stress makers (malondialdehyde, nitrotyrosine), LAU-7b compared to placebo;
- The changes from pre-study of in plasma ceramide subclass concentrations, LAU-7b compared to placebo;
- The change in plasma lipidomics (AA, DHA, AA/DHA ratio and EPA), inflammation markers, plasma oxidative stress markers, FEV₁, body weight and BMI measurements, between the start and the end of IV-treated PEx (performed only in patients who receive IV antibiotics for what their treating physician considers an exacerbation), LAU-7b compared to placebo;
- The change from pre-study in systemic bone formation/resorption markers, LAU-7b compared to placebo;
- At specific clinical sites, the change in bone density from baseline through 24 weeks of treatment, LAU-7b compared to placebo;
- At specific clinical sites, the changes in clinical scoring using the Matouk Disease Score contrasting the post-treatment score to the pre-study score, LAU-7b compared to placebo;
- Correlation of plasma retinol and retinol-binding protein levels measured during the study with ophthalmological assessments.

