9.2.4 Telephone contacts (around Days 10, 38, 66, 94, 122 and 150)

All patients will be contacted by phone on or about 10 days post-first dose of each cycle, to inquire about potential adverse events. Specific attention will be put on probing about adverse events related to visual disturbances or dermatological problems as follows: "How is your vision since the last visit/phone call?" and "How is your skin since the last visit/phone call?" Actions may be taken if necessary.

9.2.5 End-of-Cycle Visits (Visits 4, 5, 6 and 7, on Days 21(window: Days 21-22), 49(window: Days 49-51), 77(window: Days 77-79), 105 (window: Days 105-107) and 161(window: Days 161-163)

Special attention will be put on reports of symptoms/signs of pulmonary exacerbation by patients as this may trigger a set of additional assessments. Details are presented in Section 9.3 "Pulmonary Exacerbation Reporting and Evaluation". Adverse events will be monitored and captured at all visits.

1. **On Days 21, 77 and 161 visits**, the following assessments will also be done:
 - a. Focused physical examination;
 - b. Ophthalmological evaluation: The NVQ will be self-administered, and if Grade 2 severity criteria is met or exceeded (On Day 77 visit, the ophthalmological examination is planned, independently of the NVQ result), a full ophthalmological examination will be performed (includes dark adaptation tests), and if clinically indicated by the ophthalmologist, an electroretinogram will also be performed, in order to evaluate any potential ophthalmological condition developed during the treatment cycle);
 - c. Vital signs and 12-lead ECG;
 - d. Pulmonary function tests (FEV₁);
 - e. Pre-dose blood sampling and urine collection for safety laboratory tests, pregnancy test if applicable, plasma retinol and retinol-binding protein;
 - f. Study drug compliance check and concomitant medications;
 - g. Body weight, with BMI calculated.
2. **On Days 49 and 105 visits**, the following assessments will also be done;
 - a. Safety laboratory tests;
 - b. Pulmonary function test (FEV₁);
 - c. Concomitant medications.
3. **On Days 21 and 77 visits only**: All patients will return prior treatment boxes, for accountability purposes and will receive re-supply of study treatment for their next treatment cycle(s);

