Question 3. Recovery after dazzling: When you transition from a semi-obscure environment to a strongly lit one, do you remain dazzled?

Questions Q1 and Q2: Y (Yes) means normal. Questions Q3: N (No) means normal.

Assessment of the extent of reported symptoms: Level 0: no abnormal answer; Level 1: one abnormal answer; Level 2: two abnormal answers; and Level 3: three abnormal answers.

NVQ administration: Screening, Day 21, Day 77, Day 161, Day 189.

Level 1 NVQ will result in the given symptom to be considered a Grade 1 AE. However, it will not trigger an escalation to Step 2. Level 2 or 3 NVQ will automatically trigger a complete ophthalmological examination (Step 2) and its AE severity graded by the ophthalmologist.

Step 2: Complete ophthalmological examination, including specific dark adaptation tests

Administration: Screening, Day 77 and Day 189, and following any Level 2-3 NVQ report.

Suggested dark adaptation test to be included: a test able to evaluate dark-adaptation changes such as cone-rod break and the final rod threshold (see note below). Severity grading using CTCAE to be performed on confirmed nyctalopia episodes. If the reported symptoms do not get confirmed by the objective measures in Step 2, the default CTCAE severity Grade 1 will be used.

Step 3: Electroretinogram (ERG)

Administration: to be performed only if clinically indicated, in particular if the ophthalmological examination results are equivocal, or the type of signs/symptoms requires it.

Ophthalmologic examinations will be performed by (or under the oversight of) a licensed ophthalmologist at screening, Day 77 and Day 189 visits. It can also be triggered on demand if a patient reports signs of ophthalmologic nature upon questioning or at the time of the scheduled ophthalmologic questions posed on several occasions, according to the Schedule of Events, page 10.

The scheduled complete ophthalmologic examination will consist of the following: Examination of visual acuity, examination for amblyopia, examination of eyelids, conjunctiva, cornea, pupillary reactions to light and accommodation, low contrast visual function (Contrast Sensitivity), specific dark adaptation testsⁱⁱⁱ, lens,

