12 STATISTICAL ANALYSIS

A statistical analysis plan (SAP) will provide details of the methods of analysis to address all study objectives. The SAP may be amended during the course of the study, but will be finalized before the cutoff date for any analysis.

Data summaries by treatment group will be presented. For continuous variables, data will be summarized with the number of patients, mean, standard deviation, median, and minimum and maximum values by treatment group. For categorical variables, data will be tabulated in frequency tables to display the number and proportion of patients for each category by treatment group. Baseline assessments for each outcome variable will be defined as the last measurement obtained before the first dose of study drug except the baseline FEV₁ which will be the average of the screening and baseline best values, to reduce variability. Statistical significance will be set at the 5% level.

Diligent efforts will be made to prevent missing data in the study. For example, patients who discontinue the study treatment early or initiate medication changes (including those prohibited by the protocol) should still be followed for all regularly scheduled visits for safety and relevant efficacy assessments, or for a minimum of a 1-month follow-up. A clear distinction should be made between treatment discontinuation and study withdrawal. Efficacy assessments occurring after treatment discontinuation should not be included in the per-protocol analysis.

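### SAP 3.18 relates nyctalopia events to the retinol/RBP change at Week 24 only, so patients who stop drug after nyctalopia weaken the correlation; an on-treatment mean avoids this

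*SAP*

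**What the plan says.** SAP 3.18 (Additional Safety Evaluations) specifies a "Spearman correlation between plasma retinol and retinol-binding protein concentrations (change-from-baseline to Week 24) and the cumulative number of AEs" of nyctalopia, shown as scatter plots with a regression line. Events are identified by the coding path "Eye disorders/ Night blindness/ Nyctalopia". The same section states: "All safety analyses will be performed on the Safety population". It gives no on-treatment restriction, no rule for patients who stopped or interrupted drug, and no rule for a missing Day 161 sample. It does not say whether the correlation is by arm.

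The protocol is wider on timing. Section 7.1.4 lists as exploratory: "Correlation of plasma retinol and retinol-binding protein levels measured during the study with ophthalmological assessments". Section 12.5 asks for retinol and RBP values and their changes to be correlated with ophthalmological symptoms, nyctalopia in particular. Neither section limits the blood values to Week 24, and SAP Section 5 does not list that limit among the changes from protocol.

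Earlier values exist. Protocol 9.2.5 requires on Days 21, 77 and 161: "Pre-dose blood sampling and urine collection for safety laboratory tests, pregnancy test if applicable, plasma retinol and retinol-binding protein".

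Protocol 12 says that patients who discontinue treatment "should still be followed for all regularly scheduled visits for safety", but both it and Section 8.4 accept a minimum of follow-up about a month after the last dose. On recovery, Protocol 5.4.4.2 reports from earlier fenretinide trials that "plasma retinol concentrations returned to normal in one month following discontinuation of fenretinide".

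**The concern.** The two variables describe different periods. The AE count accumulates over the study. The retinol change is a snapshot of Day 161, when continuing patients are on drug and stopped patients are not. For a patient who stopped because of nyctalopia, the snapshot no longer shows the depletion that went with the event. That patient enters with counted events and little retinol change, or drops out for want of a Day 161 sample.

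This correlation is the only planned analysis that formally links retinol or RBP to an eye outcome. SAP 3.11 summarises retinol and RBP by visit, and SAP 3.10 plans no statistical analysis of ophthalmologic data. A figure pulled toward zero could be read as evidence that retinol depletion does not track night-vision symptoms, when the choice of time point produced the result.

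**Working it through.** The documents give no expected correlation, nyctalopia rate or stopping rate, so there is no plan figure to reproduce. The check has two parts.

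**Timing, from the documents.** Each cycle is 21 days on drug and 7 off (Protocol 9.4). The retinol visits fall on the last dosing day of a cycle:
- Day 21 = cycle 1.
- Day 77 = 2 × 28 + 21, cycle 3.
- Day 161 = 5 × 28 + 21, cycle 6.

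With recovery in about 28 days, anyone stopping before about Day 161 - 28 = Day 133 can be fully recovered at Day 161. Later stoppers are partly recovered. The paediatric data in Protocol 5.4.4.2 suggest partial recovery is quicker: 33% of baseline after 7 days of dosing, then 55-106% by Day 21, that is, 14 days off drug.

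An illustration with assumed values: a patient whose retinol is 40% below baseline on Days 21 and 77 has nyctalopia and stops on Day 90. Day 161 is 71 days later, so the Week 24 change is near 0 with at least one event counted. The on-treatment mean is -40%.

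**Size, by simulation.** Inputs from the documents: 136 patients, 1:1, so 68 per arm; recovery over 28 days. Assumed:
- LAU-7b nyctalopia incidence 10%, 20% or 30%; placebo 3%.
- Mean on-drug retinol fall 30% or 50% of baseline.
- Between-patient SD 15 points, visit noise SD 10 points.
- AE rate rising with depth of fall.
- A given share of affected patients stop at their first event, with linear recovery.

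There were 400 runs per scenario. Ranges are mean Spearman correlations over the incidences and falls, with every stopper sampled at Day 161:

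| Affected patients who stop | Mean number of stoppers at 20% incidence | Week 24, LAU-7b arm | Week 24, arms pooled |
|---|---|---|---|
| 0% | 0 | -0.22 to -0.36 | -0.18 to -0.38 |
| 10% | 1.1-1.2 | -0.16 to -0.27 | -0.15 to -0.34 |
| 25% | 3.0-3.1 | -0.05 to -0.14 | -0.10 to -0.25 |
| 50% | 5.9-6.0 | +0.07 to +0.15 | -0.01 to -0.12 |
| 75% | 8.9 | +0.22 to +0.40 | +0.03 to +0.08 |

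For scale, the null standard error of a Spearman correlation in 68 patients is about 1/√67 = 0.12.

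Attendance matters as well. At 50% stopping, the LAU-7b arm value is about 0 to -0.06 if half the stoppers are sampled. It is -0.16 to -0.29 if none are, which is weakened but not reversed.

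At 10% incidence there are about 0.10 × 68 = 6.8 affected patients. A 25% stopping share is then 1-2 patients, and 50% is about 3.

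With the mean on-treatment change (Days 21, 77 and 161 up to last dose) in place of the Week 24 change, the correlation stays negative in every scenario: -0.20 to -0.40 in the LAU-7b arm and -0.17 to -0.41 pooled.

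**The case against.** The strongest reply is that the damaging scenarios are unlikely. Protocol 5.4.4.3 says the effect was rarely dose limiting and quickly reversible, 5.4.4.1 calls it generally mild, and the drug-free weeks are there to prevent it. In the two neuroblastoma studies no patient stopped for toxicity. At 25-30% incidence (17-20 of 68 patients), 50-75% stopping would mean roughly 9-15 LAU-7b patients stopping for nyctalopia alone. This stands. A reader might infer that every stopper enters with recovered retinol and that the correlation will reverse. The documents do not support that: some stoppers will have no Day 161 value, and late stoppers will be only partly recovered.

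A reader might also infer that the SAP dropped the protocol's eye examinations in favour of AE reports. Protocol 12.5 already names nyctalopia symptoms, so only the Week 24 limit is new.

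A third inference is that pooling the arms would manufacture a correlation. It could, but pooling is read from silence. The mock figures were not available for this review, and Protocol 12 summarises data by treatment group as a general rule.

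Finally, the analysis is exploratory. Readers will also see retinol and RBP by visit, NVQ levels, confirmed symptoms and AEs leading to discontinuation. Those outputs would make stoppers visible, but they do not correct the correlation itself.

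**Conclusion.** The point holds as a modest one. The Week 24 change is a poor exposure measure for events accumulated over the study, and early stopping biases the correlation toward zero. If about 10% of affected patients stop and are sampled, the loss is partial. Under the assumed rates, the correlation is close to zero within the LAU-7b arm at about 25% and changes sign at about 50%. Pooled over arms, the sign changes only somewhere between 50% and 75%. Events may be few, so one to three patients can make a visible difference.

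The sizes rest on assumed incidence, stopping, attendance and variability. Recovery time is taken from earlier trials in other populations and with another formulation. The direction of the bias needs only that some affected patients stop early. Nothing here touches the FEV1 analysis.

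**What to change.** In SAP 3.18, replace the change from baseline to Week 24 with each patient's mean on-treatment change from baseline in retinol, and likewise in RBP. Use the Day 21, 77 and 161 samples taken up to the last dose. State that an end-of-cycle sample drawn inside its visit window counts as on treatment, since the Day 161 window in Protocol 9.2.5 runs to Day 163. Compute the Spearman correlation within the LAU-7b arm, plot placebo separately, and keep the Week 24 version as supportive. Record the change in SAP Section 5.

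The mean is preferable to the lowest value, which tends to be lower the more samples a patient gives and so would again make early stoppers look less depleted. The last value before the first event is undefined for patients without one.

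The cost is one derived variable from data already collected. The downside is small: early stoppers contribute fewer samples, and anyone stopping before Day 21 contributes none.
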